9.4 Responsibilities

Principal Investigator (PI) or delegate:

1. Checking for AEs and ARs when participants attend for treatment / follow-up.
2. Using medical judgement in assigning seriousness, causality and whether the event/reaction was anticipated using the Reference Safety Information approved for the trial.
3. Using medical judgement in assigning seriousness and causality and providing an opinion on whether the event/reaction was anticipated using the Reference Safety Information approved for the trial.
4. Ensuring that all SAEs are recorded and reported to the sponsor within 24 hours of becoming aware of the event and provide further follow-up information as soon as available. Ensuring that SAEs are chased with Sponsor if a record of receipt is not received within 2 working days of initial reporting.
5. Ensuring that AEs and ARs are recorded and reported to the sponsor in line with the requirements of the protocol.

Chief Investigator (CI, in this single-site study the same individual as the PI) or delegate:

1. Clinical oversight of the safety of patients participating in the trial, including an ongoing review of the risk / benefit.
2. Using medical judgement in assigning whether an event/reaction was anticipated or expected in line with the Reference Safety Information.
3. Immediate review of all SUSARs.
4. Assigning Medical Dictionary for Regulatory Activities (MedDRA) or Body System coding to all SAEs and SARs.
5. Preparing the clinical sections and final sign off of the Development Safety Update Report (DSUR).

Sponsor: (NB where relevant these can be delegated to CI)

1. Collection and verification of AEs, ARs, SAEs, SARs and SUSARs according to the trial protocol.

2. Expedited reporting of SUSARs to the Competent Authority (MHRA) and REC within required timelines.
3. Checking for (annually) and notifying PIs of updates to the Reference Safety Information for the trial.
4. Preparing standard tables and other relevant information for the DSUR in collaboration with the CI and ensuring timely submission to the MHRA and REC.

9.5 Notification of deaths

- o Any deaths will be treated as an SAE and reported accordingly to the sponsor using the SAE reporting procedures within 24 hours of becoming aware, irrespective of whether the death is related to the IMP, endotoxin administration or an unrelated event.

9.6 Pregnancy reporting

- Pregnancy is not expected to occur as women of childbearing potential will be excluded from study involvement. Nevertheless, any pregnancy occurring in a study participant should be reported to the Chief Investigator and the Sponsor using the relevant sponsor-provided Pregnancy Reporting Form within 24 hours of notification. Any pregnant participant will be withdrawn from the study. Follow-up of the pregnant participant and child born to a pregnant trial participant, if this becomes necessary, will be discussed with the sponsor in this unlikely event.
- There are no restrictions nor requirements for follow up of the children of male participants in the study.

9.7 Overdose

An overdose will be defined as any amount taken, above that prescribed, that in the opinion of a medically-qualified investigator has the potential to cause significant harm. If an overdose of a study drug occurs, then investigators or other site personnel will inform the Sponsor immediately that they become aware of it, and in any case within 24 hours. Overdoses may be observed from sachet/tablet counts or patient comment.

In case of overdose of aspirin (aspirin lysine), this will be considered equivalent to standard preparations of aspirin. Aspirin is an established agent and standard guidelines for the assessment and management of overdose should be followed.

Similarly, ticagrelor is an established drug and usual clinical procedures will be followed in the event of overdose.

Participants who receive an overdose of medication may be withdrawn from the study at the discretion of the investigators.

If an SAE is associated with the overdose, the investigators will ensure the overdose is fully described in the SAE report form.

9.8 Reporting urgent safety measures

If any urgent safety measures are taken, the CI/Sponsor shall immediately and, in any event, no later than 3 days from the date the measures are taken, give written notice to the MHRA and the relevant REC of the measures taken and the circumstances giving rise to those measures.

9.9 The type and duration of the follow-up of participants after adverse reactions.

Adverse drug reactions will be followed up by telephone or in person, as necessary, until resolved or stable.

Follow up of existing SUSARs (i.e. those which start within the reporting period) will need to be reported to the sponsor indefinitely until resolved.

9.10 Development safety update reports

The CI will provide (in addition to the expedited reporting above) DSURs once a year throughout the clinical trial, or as necessary, to the Competent Authority (MHRA), where relevant the Research Ethics Committee and the sponsor.

The report will be submitted within 60 days of the Developmental International Birth Date (DIBD) of the trial each year until the trial is declared ended.

10 STATISTICS AND DATA ANALYSIS

10.1 Sample size calculation

In our group's previous study of endotoxaemia in 30 participants receiving ticagrelor, clopidogrel or placebo, we saw, after log transformation, a mean 2 hour post-endotoxin plasma TNF- α 1.88 pg/ml with a standard deviation of 0.410 pg/ml.

There is no available raw data and no reliable estimate of the means or standard deviations of the log transformed TNF- α values for any of the three aspirin doses using the same methods. However, a study using a different endotoxin regimen has shown that aspirin 80 mg OD (which is not expected to be significantly different in effect to 75 mg OD) increased peak plasma TNF- α by around 40% compared to those receiving no drug.

We have a clear hypothesis that increasing aspirin dose increases TNF- α , therefore a one-sided test will suffice.

We estimate that clinically-relevant differences in plasma TNF- α at 2 hours post-endotoxin between the dosing regimens might be a 20% increase with 20 mg BD vs. no aspirin, 40% increase with 75 mg OD vs. no aspirin and 60% with 300 mg OD vs. no aspirin, based on the raw data.

These assumptions provide the following sample size estimate:

Test significance level, α	0.050
Number of groups, G	4
Variance of means, $V=S(m_i-m)^2 / G$	0.031
Common standard deviation, s	0.410
Effect size, $D^2 = V/s^2$	0.1828
Power (%)	80
n per group	16

Therefore, when the sample size in each of the 4 groups is 16, a one-way analysis of variance will have 80% power to detect at the 0.050 level a difference in means characterised by a Variance of means, $V=\sum(\mu_i-\mu)^2 / G$ of 0.031, assuming that the common standard deviation is 0.410.

To allow for up to 10% drop-out, the sample size per group will be 18. Drop-outs will not be replaced but it is expected that there will be at least 16 per group after withdrawals.

This sample size calculation was performed by [name] CStat, Senior Consultant, Statistical Services Unit, University of Sheffield, to whom the investigators are grateful.

10.2 Planned recruitment rate

It is aimed to recruit participants at the minimum rate of one per week. Based on our group's previous experience of similar studies, this is sensibly feasible.

10.3 Statistical analysis plan

10.3.1 Summary of baseline data and flow of patients

The following baseline data will be collected and reported:

From visit 1

- Demographic data (age, sex, ethnicity)
- Vital signs: pulse, blood pressure and temperature
- Weight and BMI
- Full blood count, urea & electrolytes, liver function tests

At visit 2

- TNF- α , IL-6, serum TXB₂, urine PGI-M, platelet aggregation responses to arachidonic acid, ADP and collagen
- Bleeding time

Categorical data will be reported as proportions and percentages. Differences between the groups will be assessed using Fisher's exact contingency test. Continuous data will be reported as mean and standard deviation if normally distributed otherwise median and interquartile range. Differences between the parallel groups will be assessed with ANOVA, with Bonferroni pairwise comparisons made if any ANOVA reaches $p<0.05$.

A CONSORT flow diagram will be prepared for inclusion in the report of study findings.

10.3.2 Primary outcome analysis

The primary endpoint will be plasma TNF- α at 2 hours following endotoxin administration assessed between aspirin groups (control vs. 20 mg BD vs. 75 mg OD vs. 300 mg OD, without ticagrelor) by one-way ANOVA with treatment as a factor.

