- Collect unused study medication and perform drug accountability check (sachet/pill count)
- Infusion of 250 ml 0.9% saline over 30 minutes
- 23 ml venous blood at 60 minutes after last dose of oral antiplatelet medication or equivalent time if not receiving IMP during period 1 (just before endotoxin administration)

0 hour (time of endotoxin injection)

- Continuous cardiac monitoring starts
- *E.coli* endotoxin 2 ng/kg intravenously administered over 1 minute
- Vital signs at 5, 15 and 30 minutes post-endotoxin
- Continuous IV infusion of 250 ml 0.9% saline over 1 hour
- 14 ml venous blood sample at 30 minutes post endotoxin

1 hour post-endotoxin injection

- Vital signs at 1 hour and 1.5 hours post endotoxin injection
- Continuous IV infusion of 250 ml 0.9% saline over 1 hour
- 14 ml venous blood sample at 1 hour post endotoxin
- Urine sample at 1 hour post endotoxin
- 14 ml venous blood sample at 1½ hours post endotoxin

2 hours post-endotoxin injection

- Vital signs at 2 hours post endotoxin

- Continuous IV infusion of 250 ml 0.9% saline over 1 hour
- 23 ml venous blood sample at 2 hours post endotoxin
- Urine sample at 2 hours post endotoxin

3 hours post-endotoxin injection

- Vital signs at 3 hours post endotoxin
- 23 ml venous blood sample at 3 hours post endotoxin
- Bleeding time measurement at 3 hours post endotoxin

4 hours post-endotoxin injection

- Vital signs at 4 hours post endotoxin
- 14 ml venous blood sample at 4 hours post endotoxin
- Urine sample at 4 hours post endotoxin

6 hours post-endotoxin injection

- Vital signs at 6 hours post endotoxin
- 14 ml venous blood sample at 6 hours post endotoxin
- Urine sample at 6 hours post endotoxin
- Continuous cardiac monitoring ends

Visit 8 (Period 2, 1 day after visit 6)

- Telephone follow-up for adverse events
- Facility to convert to in-person visit if any concerns raised

Visit 9 (Period 2, 10 to 14 days after visit 6)

- Telephone follow-up for adverse events

Study investigations will be performed at the following time points:*

*Baseline refers to visit 2, and the pre- and post-endotoxin samples are to be taken during both experimental periods.

- **Inflammatory markers and cytokines**
- TNF- α : Baseline, pre-last medication dose, pre-endotoxin and 0.5, 1, 1.5, 2, 3, 4 and 6 hours post-endotoxin
- IL-6: Baseline, pre-last medication dose, pre-endotoxin and 0.5, 1, 1.5, 2, 3, 4 and 6 hours post-endotoxin
- CRP: Baseline, pre-endotoxin and 6 hours post-endotoxin

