Additionally, continuing the study will be considered futile, and therefore discontinued, if the lower limit of the 95 % confidence interval of the mean change in TNF- α at 2 hours after endotoxin from the 300 mg aspirin OD group to no aspirin group is less than (more negative than) -2000 pg/mL.

Should neither of these criteria be met, the investigators will meet to review the results of the interim analysis and, in discussion with the Sponsor, decide on whether to continue the study, taking into account feasibility, including consideration of local and national restrictions.

Secondary analyses to be carried out in the event of premature termination

If the trial is prematurely terminated, data concerning other endpoints will then be analysed as follows, using methods taking best into account the cases of participant data missing from one period:

1. Plasma TNF- α over time following endotoxin administration (measured at 0, 0.5, 1, 1.5, 2, 3, 4 and 6 hours post-endotoxin) assessed between treatment groups (control vs. 20 mg BD vs. 75 mg OD vs. 300 mg OD, with or without ticagrelor) using a mixed effect linear model with patient as a random effect, aspirin dose, presence or absence of ticagrelor treatment and treatment period (first or second) as fixed effects, and baseline value as covariate.
2. Plasma IL-6 over time following endotoxin administration (measured at 0, 0.5, 1, 1.5, 2, 3, 4 and 6 hours post-endotoxin) assessed between treatment groups (control vs. 20 mg BD vs. 75 mg OD vs. 300 mg OD, with or without ticagrelor) using a mixed effect linear model with patient as a random effect, aspirin dose, presence or absence of ticagrelor treatment and treatment period (first or second) as fixed effects, and baseline value as covariate.
3. Change in serum CRP over time following endotoxin administration (measured at 0 and 6 hours post-endotoxin) assessed between treatment groups (control vs. 20 mg BD vs. 75 mg OD vs. 300 mg OD, with or without ticagrelor) using a mixed effect linear model with patient as a random effect, aspirin dose, presence or absence of ticagrelor treatment and treatment period (first or second) as fixed effects, and baseline value as covariate.

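### The primary and interim tests of 2-hour TNF-α use no baseline covariate, although visit-2 TNF-α is collected from every randomised participant; prespecifying it is a cheap improvement, not the repair of an error

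*Protocol*

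**What the plan says.** The primary analysis (section 10.3.2, same text in protocol and SAP) compares TNF-α at 2 hours after endotoxin between control, 20 mg BD, 75 mg OD and 300 mg OD, all without ticagrelor, "by one-way ANOVA with treatment as a factor". The interim primary test in section 10.6 is also a one-way ANOVA on these groups, and the trial stops if it gives p<0.05.

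Protocol section 7.7 schedules TNF-α at "Baseline, pre-last medication dose, pre-endotoxin and 0.5, 1, 1.5, 2, 3, 4 and 6 hours post-endotoxin", and its footnote defines baseline as visit 2. Visit 2 is the randomisation visit, before study medication starts.

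Section 10.5, headed as adjusted analysis, names no covariate and deals only with log transformation. The models that section 10.6 lists for use after premature termination do adjust. For TNF-α over time they take aspirin dose, ticagrelor and period "as fixed effects, and baseline value as covariate".

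**The concern.** The planned margin is thin. Protocol section 10.1 sizes the trial so that "a one-way analysis of variance will have 80% power to detect at the 0.050 level" with 16 per group, and the interim has only about 10 per group. A pre-drug measurement of the outcome marker is available for everyone randomised, and the test that decides the trial does not use it. The plan adjusts for a baseline value in secondary models of the same marker and gives no reason for the difference.

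There is also a question of prespecification. Section 10.3.1 plans ANOVA tests of baseline differences, TNF-α included, but does not say what follows if one is significant. In an open-label trial that uses simple randomisation, whether to adjust the primary result could then become a choice made after seeing the data. Naming the covariate now would settle it.

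**Working it through.** **Inputs.** From protocol section 10.1: effects of "20% increase with 20 mg BD vs. no aspirin, 40% increase with 75 mg OD vs. no aspirin and 60% with 300 mg OD"; "assuming that the common standard deviation is 0.410"; four groups; α = 0.05. From section 10.6: 83 endotoxin visits over eight regimens, so 83/8 ≈ 10.4 per regimen; 10 is used below. The correlation r between log visit-2 and log 2-hour TNF-α is not in the documents. It is an assumption, shown from 0 to 0.5.

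**Step 1: the plan's own figure.** The natural logs of 1, 1.2, 1.4 and 1.6 are 0, 0.182, 0.336 and 0.470. Their variance is V = 0.0307, so V/s² = 0.0307/0.410² = 0.1828, as stated. With n per group, λ = 4nV/s² and the F test has 3 and 4n−4 df. At n = 16, λ = 64 × 0.1828 = 11.70 and power is 80.2%; at n = 15 it is 77.1%. The stated 16 per group is reproduced, with no baseline adjustment in it. At n = 10 the unadjusted power is 55.9%.

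**Step 2: adjustment, counting only the lost df.** The residual variance becomes s²(1−r²), so λ becomes λ/(1−r²), with 3 and 4n−5 df. At n = 16 and r = 0 this gives 80.18% against 80.23%, an apparent cost of less than 0.1 point. The calculation is too favourable. It ignores the variance added when the covariate is unbalanced between groups by chance and its slope has to be estimated.

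**Step 3: simulation, which includes that imbalance.** Same effects and SD, standard normal covariate, 20,000 trials per case. The Monte Carlo standard error is √(0.8×0.2/20,000) ≈ 0.3 point, so small differences between rows should not be over-read.

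| Model | 16/group, df only | 16/group, simulated | 10/group, df only | 10/group, simulated |
|---|---|---|---|---|
| Unadjusted | 80.2% | about 80% | 55.9% | about 56% |
| Covariate, r = 0 | 80.2% | 79–80% | 55.8% | about 54.5% |
| Covariate, r = 0.1 | 80.6% | 79–80% | 56.2% | about 55% |
| Covariate, r = 0.2 | 81.9% | about 81% | 57.7% | 56–57% |
| Covariate, r = 0.3 | 84.1% | 83–84% | 60.2% | 58–59% |
| Covariate, r = 0.5 | 90.9% | 90–91% | 69.6% | about 68% |

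Counting df alone, break-even is at r ≈ 0.03. In the simulation it lies between 0.1 and 0.2 at both sizes.

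**Step 4: adding a period term as well.** With r = 0, no true period effect and period assigned at random, one set of runs gave, for unadjusted / covariate / covariate plus period, 80.9 / 80.3 / 79.2% at 16 per group and 55.9 / 54.5 / 53.4% at 10 per group. Period costs about 1 further point in each case. The total loss is 80.9 − 79.2 = 1.7 points at full size and 55.9 − 53.4 = 2.5 points at the interim.

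**Step 5: which baseline.** Section 7.7 defines baseline as visit 2, but it also describes the pre-dose blood sample on the endotoxin day as baseline, and so does Appendix 1. In the aspirin groups that sample follows 10–14 days of aspirin. A covariate measured after treatment has started can absorb part of the treatment effect, so only the visit-2 value is safe here. Section 10.6 does not say which it means.

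**The case against.** The strongest reply is that an unadjusted ANOVA in a randomised comparison is valid, controls type I error, and is exactly the test the sample size was built on. That stands in full.

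The second reply is that r may be small. The covariate is an unstimulated level in screened healthy volunteers, whereas the outcome is induced by endotoxin. For participants whose no-ticagrelor day comes second, visit 2 precedes it by roughly 10+35+10 = 55 to 14+126+14 = 154 days. Nothing in the documents supports r of 0.3 to 0.5, where the attractive gains lie. This also stands: the gain cannot be quantified from the documents.

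Two stronger readings are tempting. A reader might infer that the plan leaves free precision unused. Steps 3 and 4 show otherwise: if baseline does not predict the response, adjustment has a small real cost, which the df-only figure hides. A reader might also infer that the plan contradicts itself by adjusting in section 10.6 but not in 10.3.2. The adjusted models there are secondary, run only after early termination, and pool both periods with and without ticagrelor, so they need terms that the primary test does not. The interim and final primary tests agree with each other.

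What the reply does not remove is the asymmetry between a loss of about 1 point at worst for the covariate at full size and a gain of several points if r is moderate, or the value of settling the adjustment in advance.

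**Conclusion.** The point holds as a recommended improvement. The primary and interim tests could use a pre-drug measurement that is already collected, and the plan does not say why they do not. At 16 per group the covariate changes power by between a loss of up to 1 point (r = 0) and a gain of about 10 points (r = 0.5), with about 3 points at r = 0.3. At about 10 per group the range runs from a loss of about 1.5 points to a gain of about 12. Gains appear at r of about 0.2 or more.

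These figures rest on the assumed r, on the plan's effects, and on reading the SD of 0.410 as a natural-log value. V reproduces only with natural logs, and section 10.1 does not state the base for the SD. The documents do not support calling the present analysis invalid, biased or internally contradictory.

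**What to change.** In section 10.3.2 and the interim part of section 10.6, in both documents, prespecify ANCOVA of log 2-hour TNF-α with aspirin group as factor and log visit-2 TNF-α as covariate. Name visit 2 explicitly, so that the endotoxin-day pre-dose sample cannot be used instead. Keep the unadjusted one-way ANOVA as a sensitivity analysis. Extend section 10.8 to say how a visit-2 value that is missing, or too low to be logged, will be handled. If the sponsor prefers the unadjusted test, one sentence giving the reason would be enough.

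A term for the period of the no-ticagrelor day is optional: it guards against a period effect and costs about 1 further point of power if there is none.

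The cost is about one sentence in each of these places, one df and no new data. The named downside is a loss of up to about 1 point of power at full size if baseline does not predict the response, and about 2 to 2.5 points at the interim if period is added too. The change should be fixed before 2-hour results are linked to allocation.

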10.3.3 Secondary outcome analysis

Secondary analyses will be as follows:

Between aspirin dose regimens

1. Plasma TNF- α over time following endotoxin administration (measured at 0, 0.5, 1, 1.5, 2, 3, 4 and 6 hours post-endotoxin) assessed between aspirin groups (control vs. 20 mg BD vs. 75 mg OD vs. 300 mg OD, without ticagrelor) by two-way mixed ANOVA with treatment as a between-subjects factor and timepoint as a within-subjects factor.
2. Plasma IL-6 at 2 hours following endotoxin administration assessed between aspirin groups (control vs. 20 mg BD vs. 75 mg OD vs. 300 mg OD, without ticagrelor) by one-way ANOVA with treatment as a factor.
3. Plasma IL-6 over time following endotoxin administration (measured at 0, 0.5, 1, 1.5, 2, 3, 4 and 6 hours post-endotoxin) assessed between aspirin groups (control vs. 20 mg BD vs. 75 mg OD vs. 300 mg OD, without ticagrelor) by two-way mixed ANOVA with treatment as a between-subjects factor and timepoint as a within-subjects factor.
4. Change in serum CRP over time following endotoxin administration (measured at 0 and 6 hours post-endotoxin) assessed between aspirin groups (control vs. 20 mg BD vs. 75 mg OD vs. 300 mg OD, without ticagrelor) by one-way ANOVA.
5. Serum TXB₂ over time following endotoxin administration (measured at 0, 0.5, 1, 1.5, 2, 3, 4 and 6 hours post-endotoxin) assessed between aspirin groups (control vs. 20 mg BD vs. 75 mg OD vs. 300 mg OD, without ticagrelor) by two-way mixed ANOVA with treatment as a between-subjects factor and timepoint as a within-subjects factor.
6. Urinary PGI-M (measured at 0, 2, 4 and 6 hours, each adjusted for [divided by] urinary creatinine) over time following endotoxin administration assessed between aspirin groups (control vs. 20 mg BD vs. 75 mg OD vs. 300 mg OD, without ticagrelor) by two-way mixed ANOVA with treatment as a between-subjects factor and timepoint as a within-subjects factor.
7. Serum PGE₂ over time following endotoxin administration (measured at 0, 0.5, 1, 1.5, 2, 3, 4 and 6 hours post-endotoxin) assessed between aspirin groups (control vs. 20 mg BD vs. 75 mg OD vs. 300 mg OD, without ticagrelor) by two-way mixed ANOVA with treatment as a between-subjects factor and timepoint as a within-subjects factor.
8. Circulating leukocyte count over time following endotoxin administration (measured at 0, 0.5, 1, 1.5, 2, 3, 4 and 6 hours post-endotoxin) assessed between aspirin groups (control vs. 20 mg BD vs. 75 mg OD vs. 300 mg OD, without ticagrelor) by two-way mixed ANOVA with treatment as a between-subjects factor and timepoint as a within-subjects factor.

9. AUC of the graph of bleeding time following endotoxin administration (measured at 0 and 6 hours post-endotoxin) assessed between aspirin groups (control vs. 20 mg BD vs. 75 mg OD vs. 300 mg OD, without ticagrelor) by one-way ANOVA.
10. AUC of the graphs of platelet aggregation to arachidonic acid (0.3 and 1 mmol/L), collagen (4 and 16 µg/ml) and ADP (20 µmol/L) over time following endotoxin administration (measured at 0 and 6 hours post-endotoxin) assessed between aspirin groups (control vs. 20 mg BD vs. 75 mg OD vs. 300 mg OD, without ticagrelor) by one-way ANOVA.

Between DAPT regimens:

11. Plasma TNF- α at 2 hours following endotoxin administration assessed between aspirin groups (control vs. 20 mg BD vs. 75 mg OD vs. 300 mg OD, given in combination with ticagrelor) by one-way ANOVA with treatment as a factor.
12. Plasma TNF- α over time following endotoxin administration (measured at 0, 0.5, 1, 1.5, 2, 3, 4 and 6 hours post-endotoxin) assessed between aspirin groups (control vs. 20 mg BD vs. 75 mg OD vs. 300 mg OD, given in combination with ticagrelor) by two-way mixed ANOVA with treatment as a between-subjects factor and timepoint as a within-subjects factor.
13. Plasma IL-6 at 2 hours following endotoxin administration assessed between aspirin groups (control vs. 20 mg BD vs. 75 mg OD vs. 300 mg OD, given in combination with ticagrelor) by one-way ANOVA with treatment as a factor.
14. Plasma IL-6 over time following endotoxin administration (measured at 0, 0.5, 1, 1.5, 2, 3, 4 and 6 hours post-endotoxin) assessed between aspirin groups (control vs. 20 mg BD vs. 75 mg OD vs. 300 mg OD, given in combination with ticagrelor) by two-way mixed ANOVA with treatment as a between-subjects factor and timepoint as a within-subjects factor.
15. Change in serum CRP over time following endotoxin administration (measured at 0 and 6 hours post-endotoxin) assessed between aspirin groups (control vs. 20 mg BD vs. 75 mg OD vs. 300 mg OD, given in combination with ticagrelor) by one-way ANOVA.
16. Serum TXB₂ over time following endotoxin administration (measured at 0, 0.5, 1, 1.5, 2, 3, 4 and 6 hours post-endotoxin) assessed between aspirin groups (control vs. 20 mg BD vs. 75 mg OD vs. 300 mg OD, given in combination with ticagrelor) by two-way mixed ANOVA with treatment as a between-subjects factor and timepoint as a within-subjects factor.
17. Urinary PGI-M (measured at 0, 2, 4 and 6 hours, each adjusted for [divided by] urinary creatinine) over time following endotoxin administration assessed between aspirin groups (control vs. 20 mg BD vs. 75 mg OD vs. 300 mg OD, given in combination with ticagrelor) by two-way mixed ANOVA with treatment as a between-subjects factor and timepoint as a within-subjects factor.
18. Serum PGE₂ over time following endotoxin administration (measured at 0, 0.5, 1, 1.5, 2, 3, 4 and 6 hours post-endotoxin) assessed between aspirin groups (control vs. 20 mg BD vs. 75 mg OD vs. 300 mg OD, given in combination with ticagrelor) by two-way mixed ANOVA with treatment as a between-subjects factor and timepoint as a within-subjects factor.
19. Circulating leukocyte count over time following endotoxin administration (measured at 0, 0.5, 1, 1.5, 2, 3, 4 and 6 hours post-endotoxin) assessed between aspirin groups (control vs. 20 mg BD vs.

75 mg OD vs. 300 mg OD, given in combination with ticagrelor) by two-way mixed ANOVA with treatment as a between-subjects factor and timepoint as a within-subjects factor.

20. AUC of the graph of bleeding time following endotoxin administration (measured at 0 and 3 hours post-endotoxin) assessed between aspirin groups (control vs. 20 mg BD vs. 75 mg OD vs. 300 mg OD, given in combination with ticagrelor) by one-way mixed ANOVA.
21. AUC of the graphs of platelet aggregation to arachidonic acid (0.3 and 1 mmol/L), collagen (4 and 16 µg/ml) and ADP (20 µmol/L) over time following endotoxin administration (measured at 0 and 3 hours post-endotoxin) assessed between aspirin groups (control vs. 20 mg BD vs. 75 mg OD vs. 300 mg OD, given in combination with ticagrelor) by one-way ANOVA.

To compare aspirin monotherapy with aspirin and ticagrelor in combination:

1. Plasma TNF- α at 2 hours following endotoxin administration) compared between each aspirin regimen (control, 20 mg BD, 75 mg OD, 300 mg OD, each without ticagrelor) and each corresponding DAPT regimen (control, 20 mg BD, 75 mg OD, 300 mg OD, each with ticagrelor 90 mg BD) by paired t-tests.
2. AUC of the graph of plasma TNF- α over time following endotoxin administration (measured at 0, 0.5, 1, 1.5, 2, 3, 4 and 6 hours post-endotoxin) compared between each aspirin regimen (control, 20 mg BD, 75 mg OD, 300 mg OD, each without ticagrelor) and each corresponding DAPT regimen (control, 20 mg BD, 75 mg OD, 300 mg OD, each with ticagrelor 90 mg BD) by paired t-tests.
3. Plasma IL-6 at 2 hours following endotoxin administration, compared between each aspirin regimen (control, 20 mg BD, 75 mg OD, 300 mg OD, each without ticagrelor) and each corresponding DAPT regimen (control, 20 mg BD, 75 mg OD, 300 mg OD, each with ticagrelor 90 mg BD) by paired t-tests.
4. AUC of the graph of plasma IL-6 over time following endotoxin administration (measured at 0, 0.5, 1, 1.5, 2, 3, 4 and 6 hours post-endotoxin) compared between each aspirin regimen (control, 20 mg BD, 75 mg OD, 300 mg OD, each without ticagrelor) and each corresponding DAPT regimen (control, 20 mg BD, 75 mg OD, 300 mg OD, each with ticagrelor 90 mg BD) by paired t-tests.
5. Change in serum CRP over time following endotoxin administration (measured at 0 and 6 hours post-endotoxin) compared between each aspirin regimen (control, 20 mg BD, 75 mg OD, 300 mg OD, each without ticagrelor) and each corresponding DAPT regimen (control, 20 mg BD, 75 mg OD, 300 mg OD, each with ticagrelor 90 mg BD) by paired t-tests.
6. AUC of the graph of serum TXB₂ over time following endotoxin administration (measured at 0, 0.5, 1, 1.5, 2, 3, 4 and 6 hours post-endotoxin) compared between each aspirin regimen (control, 20 mg BD, 75 mg OD, 300 mg OD, each without ticagrelor) and each corresponding DAPT regimen (control, 20 mg BD, 75 mg OD, 300 mg OD, each with ticagrelor 90 mg BD) by paired t-tests.
7. AUC of the graph of urinary PGI-M (measured at 0, 2, 4 and 6 hours, each adjusted for [divided by] urinary creatinine) over time following endotoxin administration compared between each aspirin regimen (control, 20 mg BD, 75 mg OD, 300 mg OD, each without ticagrelor) and each corresponding DAPT regimen (control, 20 mg BD, 75 mg OD, 300 mg OD, each with ticagrelor 90 mg BD) by paired t-tests.
8. AUC of the graph of serum PGE₂ over time following endotoxin administration (measured at 0, 0.5, 1, 1.5, 2, 3, 4 and 6 hours post-endotoxin) compared between each aspirin regimen (control, 20 mg

BD, 75 mg OD, 300 mg OD, each without ticagrelor) and each corresponding DAPT regimen (control, 20 mg BD, 75 mg OD, 300 mg OD, each with ticagrelor 90 mg BD) by paired t-tests.

9. AUC of the graph of circulating leukocyte count over time following endotoxin administration (measured at 0, 0.5, 1, 1.5, 2, 3, 4 and 6 hours post-endotoxin) compared between each aspirin regimen (control, 20 mg BD, 75 mg OD, 300 mg OD, each without ticagrelor) and each corresponding DAPT regimen (control, 20 mg BD, 75 mg OD, 300 mg OD, each with ticagrelor 90 mg BD) by paired t-tests.
10. AUC of the graph of bleeding time following endotoxin administration (measured at 0 and 3 hours post-endotoxin) compared between each aspirin regimen (control, 20 mg BD, 75 mg OD, 300 mg OD, each without ticagrelor) and each corresponding DAPT regimen (control, 20 mg BD, 75 mg OD, 300 mg OD, each with ticagrelor 90 mg BD) by paired t-tests.
11. AUC of the graphs of platelet aggregation to arachidonic acid (0.3 and 1 mmol/L), collagen (4 and 16 µg/ml) and ADP (20 µmol/L) over time following endotoxin administration (measured at 0 and 3 hours post-endotoxin) compared between each aspirin regimen (control, 20 mg BD, 75 mg OD, 300 mg OD, each without ticagrelor) and each corresponding DAPT regimen (control, 20 mg BD, 75 mg OD, 300 mg OD, each with ticagrelor 90 mg BD) by paired t-tests.

And to model the effects of all variables (considering parallel groups):

12. Plasma TNF-α over time following endotoxin administration (measured at 0, 0.5, 1, 1.5, 2, 3, 4 and 6 hours post-endotoxin) compared between each aspirin regimen (control, 20 mg BD, 75 mg OD, 300 mg OD, each without ticagrelor) and each corresponding DAPT regimen (control, 20 mg BD, 75 mg OD, 300 mg OD, each with ticagrelor 90 mg BD) with a mixed three-way ANOVA with aspirin-dose and presence or absence of ticagrelor as between-subjects factors and timepoint as a within-subject factor.
13. Plasma IL-6 over time following endotoxin administration (measured at 0, 0.5, 1, 1.5, 2, 3, 4 and 6 hours post-endotoxin) compared between each aspirin regimen (control, 20 mg BD, 75 mg OD, 300 mg OD, each without ticagrelor) and each corresponding DAPT regimen (control, 20 mg BD, 75 mg OD, 300 mg OD, each with ticagrelor 90 mg BD) with a mixed three-way ANOVA with aspirin-dose and presence or absence of ticagrelor as between-subjects factors and timepoint as a within-subject factor.
14. Change in serum CRP over time following endotoxin administration (measured at 0 and 6 hours post-endotoxin) compared between each aspirin regimen (control, 20 mg BD, 75 mg OD, 300 mg OD, each without ticagrelor) and each corresponding DAPT regimen (control, 20 mg BD, 75 mg OD, 300 mg OD, each with ticagrelor 90 mg BD) with a mixed three-way ANOVA with aspirin-dose and presence or absence of ticagrelor as between-subjects factors and timepoint as a within-subject factor.
15. Serum TXB₂ over time following endotoxin administration (measured at 0, 0.5, 1, 1.5, 2, 3, 4 and 6 hours post-endotoxin) compared between each aspirin regimen (control, 20 mg BD, 75 mg OD, 300 mg OD, each without ticagrelor) and each corresponding DAPT regimen (control, 20 mg BD, 75 mg OD, 300 mg OD, each with ticagrelor 90 mg BD) with a mixed three-way ANOVA with aspirin-dose and presence or absence of ticagrelor as between-subjects factors and timepoint as a within-subject factor.

16. Urinary PGI-M (measured at 0, 2, 4 and 6 hours, each adjusted for [divided by] urinary creatinine) over time following endotoxin administration compared between each aspirin regimen (control, 20 mg BD, 75 mg OD, 300 mg OD, each without ticagrelor) and each corresponding DAPT regimen (control, 20 mg BD, 75 mg OD, 300 mg OD, each with ticagrelor 90 mg BD) with a mixed three-way ANOVA with aspirin-dose and presence or absence of ticagrelor as between-subjects factors and timepoint as a within-subject factor.
17. Serum PGE₂ over time following endotoxin administration (measured at 0, 0.5, 1, 1.5, 2, 3, 4 and 6 hours post-endotoxin) compared between each aspirin regimen (control, 20 mg BD, 75 mg OD, 300 mg OD, each without ticagrelor) and each corresponding DAPT regimen (control, 20 mg BD, 75 mg OD, 300 mg OD, each with ticagrelor 90 mg BD) with a mixed three-way ANOVA with aspirin-dose and presence or absence of ticagrelor as between-subjects factors and timepoint as a within-subject factor.
18. Circulating leukocyte count over time following endotoxin administration (measured at 0, 0.5, 1, 1.5, 2, 3, 4 and 6 hours post-endotoxin) compared between each aspirin regimen (control, 20 mg BD, 75 mg OD, 300 mg OD, each without ticagrelor) and each corresponding DAPT regimen (control, 20 mg BD, 75 mg OD, 300 mg OD, each with ticagrelor 90 mg BD) with a mixed three-way ANOVA with aspirin-dose and presence or absence of ticagrelor as between-subjects factors and timepoint as a within-subject factor.
19. Bleeding time following endotoxin administration (measured at 0 and 3 hours post-endotoxin) compared between each aspirin regimen (control, 20 mg BD, 75 mg OD, 300 mg OD, each without ticagrelor) and each corresponding DAPT regimen (control, 20 mg BD, 75 mg OD, 300 mg OD, each with ticagrelor 90 mg BD) with a mixed three-way ANOVA with aspirin-dose and presence or absence of ticagrelor as between-subjects factors and timepoint as a within-subject factor.
20. Platelet aggregation to arachidonic acid (0.3 and 1 mmol/L), collagen (4 and 16 µg/ml) and ADP (20 µmol/L) over time following endotoxin administration (measured at 0 and 3 hours post-endotoxin) compared between each aspirin regimen (control, 20 mg BD, 75 mg OD, 300 mg OD, each without ticagrelor) and each corresponding DAPT regimen (control, 20 mg BD, 75 mg OD, 300 mg OD, each with ticagrelor 90 mg BD) with a mixed three-way ANOVA with aspirin-dose and presence or absence of ticagrelor as between-subjects factors and timepoint as a within-subject factor.

For all endpoints (primary and secondary) tested with ANOVA, pairwise comparisons with Bonferroni correction will be used to explore relationships further where the prespecified test suggests significant differences between the groups (p<0.05).

